6.5 Multiplicity and Family-Wise Error

No methods to account for multiplicity (alpha sharing plan) will be used as this is a hypothesis generating rather than a confirmatory study.

6.6 Missing Data

When using weekly averages (P1), we will take the median of the existing values for that week and use that value to impute the missing values for patients.

Weekly missing values will be handled using Multiple Imputation (MI) approach.

No imputation for S1 and S3.

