## 6 CRITERIA FOR PARTICIPANT WITHDRAWAL OR STUDY INTERVENTION DISCONTINUATION

### 6.1 PARTICIPANT DISCONTINUATION OR WITHDRAWAL

Each enrolled subject shall remain in the clinical investigation until completion of the required follow-up period; however, a subject's participation in any clinical investigation is voluntary and the subject has the right to withdraw at any time without penalty or loss of benefit. Conceivable reasons for discontinuation may include, but not limited to, the following:

- Subject death
- Subject voluntary withdrawal
- Subject lost to follow-up as described below

The sponsor must be notified of the reason(s) for subject discontinuation. The site will provide this information to the Sponsor. Investigators must also report this to the IRB.

No additional follow-up will be required or data recorded from subjects once withdrawn from the clinical investigation, except for the vital status (deceased/alive).

However, if a subject withdraws from the investigation due to problems related to safety, the investigator shall ask for the subject's permission to follow his/her status/condition outside of the clinical investigation.

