## 11.8 ENDPOINT ANALYSIS

### 11.8.1 PRIMARY ENDPOINT ANALYSIS

General statistical approach to primary endpoint: This endpoint will be analyzed in both the ITT and PP populations. Missing data will be handled as described in Section 11.12.

Analysis strategy for P1:

The outcome variable for this objective is the median Abbott ICD and CRT-D device measured daily PA obtained over the 1 week before randomization (baseline) and week 4, week 8, and week 12 after randomization. This endpoint represents a summary measure. The hypothesis test will evaluate whether the trajectory of the mean Abbott ICD and CRT-D device measured in the remote CR treatment group is different from the trajectory in the usual management group. The test will be a multilevel modeling (aka mixed models) on trajectories of the outcomes over the study period.

P1: Compare the trajectory of the median Abbott ICD and CRT-D device measured daily PA obtained over the 1 week before randomization (baseline) and week 4, week 8, and week 12 after randomization among patients randomized to remote CR versus usual management.

Reporting for P1: Descriptive summaries of the median physical activity at baseline and 4 weeks, 8 weeks, and 12 weeks after randomization will be presented by treatment group. The estimated differences in slopes of trajectories from CR and usual care treatment groups will be presented, along with the p-values by comparing the trajectories over study period. If differences are noted with regard to baseline covariates adjusted analyses will be performed for the primary endpoint.

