6 STATISTICAL ANALYSIS

6.1 General Considerations

6.1.1 General Analysis Conventions

Categorical variables will be presented as counts and percentages of non-missing values. Continuous variables will be presented as means, standard deviations, medians, as well as minimums and maximums, and the number of non-missing values. Missing data will be handled as outlined in section 6.8. Unscheduled assessments will not be included in analyses, but may be included in listings. Appropriate rounding will be performed for the summary statistics. The number of significant digits for the mean and standard deviation will be one and two more than the number for the reported values, respectively. Minimum and maximum values will be presented with the same precision as the original data. Percentages will be presented with one decimal. All statistical tests will be two sided unless stated otherwise. Histograms will be used to assess the normality of the data. Unless otherwise specified below, baseline values will be the last collected value prior to device use.

Statistical tests used will be two-sided, with $\alpha=0.05$ as the level of significance. An absolute magnitude of the correlation coefficient that is 0.1-0.29 indicating weak correlation, 0.3-0.49 as moderate correlation and 0.5-1.0 as strong correlation.

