6.3 Primary Endpoint Analyses

P1: Compare the trajectory of the median Abbott ICD and CRT-D device measured daily PA obtained over the 1 month before randomization (baseline) and week 4, week 8, and week 12 after randomization among patients randomized to remote CR versus usual management.

Analysis strategy for P1: The outcome variable for this objective is the median Abbott ICD and CRT-D device measured daily PA obtained over the 1 month before randomization (baseline) and week 4, week 8, and week 12 after randomization. This endpoint represents a summary measure. The hypothesis test will evaluate whether the trajectory of the mean Abbott ICD and CRT-D device measured in the remote CR treatment group is different from the trajectory in the usual management group. The test will be a multilevel modeling (aka mixed models) on trajectories of the outcomes over the study period. In the multilevel model, time (week of study), treatment group, and the interaction between treatment group and time will be handled as fixed effects. Time will be modeled as a continuous variable. The model will include random effects for subject-specific intercepts and slopes, with unstructured covariance for random intercepts and slopes.

Reporting for P1: Descriptive summaries of the median physical activity at baseline and 4 weeks, 8 weeks, and 12 weeks after randomization will be presented by treatment group. The estimated difference in slopes of trajectories from the CR and usual care treatment groups will be presented, along with the p-value for comparing the trajectories over the study period. If differences are noted with regard to baseline covariates adjusted analyses will be performed for the primary endpoint.

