6.7 Sensitivity Analysis

The sensitivity Analysis will be considered for P1 ITT analysis:

Multilevel modeling after imputing missing data using MI: This sensitivity analysis will be performed with the same method as the main analysis, but with imputation for missing data as described above.

Multilevel modeling assumption not met: This sensitivity analysis will be performed if the Multilevel modeling assumptions are severely violated and data transformation is needed. If that is the case, we will run the multilevel model on the transformed data and the p-value will be compared to the main results. The estimated differences in slopes of trajectories and respective p-values will be presented.

Multilevel modeling of endpoints P1 after adjusting for baseline data: This sensitivity analysis will be performed using same methods as original analysis, but adjusting for the baseline mean in the model as a covariate. The significance of the treatment assignment variable will be tested. The estimated adjusted difference in slopes of trajectories and respective p-value will be presented and compared to the main results.

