7 TABLES, FIGURES, AND LISTINGS

Table	Title	Population
1. Disposition		
Table 1	Subject Enrollment and Status Summary	All enrolled
2. Demographics and Past Medical History		
Table 2.1	Demographics and Baseline Characteristics	ITT
Table 2.2	Demographics and Baseline Characteristics	AT
Table 2.3	Medical History at Baseline	ITT
Table 2.4	Medical History at Baseline	AT
3. Primary Endpoint Analysis		
Table 3.1.1	Primary Endpoint P1: Trajectory of the median Abbott ICD and CRT-D device measured daily PA obtained over baseline and treatment period	ITT
Table 3.1.2	Primary Endpoint P1: Descriptive statistics of the median Abbott ICD and CRT-D device measured daily PA obtained over baseline and treatment period	ITT
Table 3.2.1	Primary Endpoint P1: Trajectory of the median Abbott ICD and CRT-D device measured daily PA obtained over baseline and treatment period	AT
Table 3.2.2	Primary Endpoint P1: Descriptive statistics of the median Abbott ICD and CRT-D device measured daily PA obtained over baseline and treatment period	AT
Table 3.3	P1: Sensitivity Analysis for Imputed Data	ITT
Table 3.4*	P1: Sensitivity Analysis for Transformed Data	ITT
4. Secondary Endpoint Analysis		
Table 4.1.1	Secondary Endpoint S1: Change from baseline KCCQ HF symptom severity score to the last week of study	ITT
Table 4.1.2	Secondary Endpoint S1: Change from baseline KCCQ HF symptom severity score to the last week of study	AT
List 4.2	Secondary Endpoint S2: Adverse Events: heart failure hospitalization, fracture, myocardial infarction, serious adverse arrhythmia, and ICD therapy	ITT and AT
Table 4.3.1	Secondary Endpoint S3: Association between daily PA measured by the Abbott ICD or CRT-D device and in KCCQ HF symptoms severity score measured between baseline and end of follow up	ITT
Table 4.3.2	Secondary Endpoint S3: Association between daily PA measured by the Abbott ICD or CRT-D device and in KCCQ HF symptoms severity score measured between baseline and end of follow up	AT

*These tables will be intentionally blank if sensitivity analysis unnecessary.

Figure	Title	Population
Figure 3.1.1	Predicted Trajectories of the Mean Abbott ICD and CRT-D Device Measured Daily PA by Random Group	ITT
Figure 3.1.2	Trend of the Median Abbott ICD and CRT-D Device Measured Daily PA by Random Group	ITT
Figure 3.2.1	Predicted Trajectories of the Mean Abbott ICD and CRT-D Device Measured Daily PA by Random Group	AT

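### The documents disagree on whether the main P1 analysis imputes missing weeks, and unless it uses an across-patient fill, no planned analysis tests the missing-at-random assumption

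*SAP*

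**What the plan says.** The rule for missing P1 data appears in several places.

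- **SAP 6.6** has two sentences on P1. For weekly averages, "we will take the median of the existing values for that week and use that value to impute the missing values for patients". Then: "Weekly missing values will be handled using Multiple Imputation (MI) approach". Neither is limited to a sensitivity analysis. The section goes on to exclude imputation for S1 and S3 only.
- **Protocol 11.8.1**, on the primary endpoint: "Missing data will be handled as described in Section 11.12". Protocol 11.12 carries the same two P1 sentences as SAP 6.6. SAP 5.1 declares no departure from the protocol that affects the analysis.
- **SAP 6.7** (and Protocol 11.11) lists MI as a sensitivity analysis for P1: "This sensitivity analysis will be performed with the same method as the main analysis, but with imputation for missing data as described above". Its output is Table 3.3, "P1: Sensitivity Analysis for Imputed Data", separate from the main Table 3.1.1.
- **SAP 6.3** defines the main model and is silent on missing data: "The model will include random effects for subject-specific intercepts and slopes, with unstructured covariance for random intercepts and slopes".
- **SAP 6.1.1** says "Missing data will be handled as outlined in section 6.8", but 6.8 is the section on confounding variables.

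On how weeks go missing, Protocol 6.1 states "No additional follow-up will be required or data recorded from subjects once withdrawn", apart from vital status. Protocol 6.2 censors patients lost to follow-up at the last contact.

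**The concern.** Two programmers working from this text could produce different primary results, in a trial where the study team is unblinded. The choice should not be left until the data are in hand.

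The second issue is what the sensitivity analysis can show. Patients who withdraw or lose contact are those whose later activity is unseen, and their activity may differ from that of otherwise similar patients who stay. The reader of Table 3.3 will expect it to show how far the result depends on those unseen weeks. Under Protocol 11.3 and SAP 4.1.1 the ITT result for P1 decides whether the study succeeded, and Protocol 9.1 says the results will be used to design a pivotal trial.

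**Working it through.** **1. Three readings of the text.**

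- *Reading A: MI is in the main analysis* (SAP 6.6, Protocol 11.8.1 with 11.12). Table 3.3 is then the same analysis, differing only through the random imputation draws.
- *Reading B: the main analysis is the likelihood mixed model on observed weeks* (SAP 6.3, 6.7, Table 3.3). Standard MI then makes essentially the same missing-at-random assumption.
- *Reading C: the median sentence in 6.6 means a single fill across patients.* MI then differs from the main analysis.

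If the fill is instead for missing days within a patient's own week, it leaves that week's median unchanged, and only A and B remain.

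The other two P1 sensitivity analyses in SAP 6.7 concern transformation and baseline adjustment, not missingness.

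**2. The plan's own power figure.** Inputs from SAP 4.2: 28 patients 1:1, four time points, 15 min/day at week 12, SD 19, within-subject correlation 0.7, alpha 0.05. SAP 6.1.1 makes tests two-sided. Take times as 0, 1, 2, 3, so the sum of squares about the mean is 5.

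- SD of a patient's slope = 19 × √(0.3/5) = 4.65
- Slope difference = 15/3 = 5
- SE = 4.65 × √(2/14) = 1.76
- Power = Φ(5/1.76 − 1.96) = Φ(0.88) = 81.1%, as stated

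**3. Illustration on those inputs.** Dropout is assumed. Let CR rise linearly (0, 5, 10, 15 at baseline and weeks 4, 8, 12) and usual care stay flat. A fraction f of CR patients is lost after week 4 and is truly back at baseline from week 8.

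- True week-12 difference = (1 − f) × 15, which is 12.75 at f = 15% and 10.5 at f = 30%.
- The lost patients' observed values (0 and 5) lie on the same line as everyone else's. A missing-at-random analysis therefore continues that line and reports 15.0 at both loss rates.
- Overstatement: 15.0 − 12.75 = 2.25, and 15.0 − 10.5 = 4.5 min/day.

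**4. Does MI agree with the mixed model?** Simulation with the same effect, SD and correlation, samples of 2,000 to 3,000; MI by regression on arm and earlier values. Entries are week-12 differences in min/day.

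| Mechanism | Missing at week 12 | Complete data | Mixed model | MI |
|---|---|---|---|---|
| At random | 19% | true 15 | 15.95 | 15.90 |
| At random | 30% | true 15 | 14.87 | 14.99 |
| At random | 40% | true 15 | 14.70 | 14.76 |
| Not at random, CR only | 31% of CR | 15.67 | 18.05 | 17.93 |
| Not at random, CR only | 40% of CR | 16.11 | 19.52 | 18.99 |
| Not at random, CR only | 47% of CR | 14.71 | 19.08 | 18.14 |

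In the last three rows both methods exceed the complete-data value by about 2 to 4 min/day, while differing from each other by less than 1. Agreement between them would not reveal the error.

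Under Reading C, an across-patient fill in the first three rows gave 12.8, 11.0 and 7.8, well away from MI.

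**5. Does a delta shift respond?** In the row with 40% of CR missing, lowering imputed CR values by 5, 10 and 15 min/day moved the estimate from 18.99 to 17.05, 14.89 and 12.81.

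**6. Precision.** With complete data and 28 patients, the SE of the week-12 difference is 3 × 1.76 = 5.28, a 95% half-width of about 10.3. SAP 4.1 gives 13 patients; with 6 and 7 per arm the SE is 3 × 4.65 × √(1/6 + 1/7) = 7.77, a half-width of about 15.2.

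**The case against.** The SAP can be reconciled. Section 6.3 specifies a mixed model with no imputation, 6.7 refers back to 6.6 for its imputation method, and Table 3.3 is separate. The natural reading is a likelihood main analysis with MI as sensitivity. This is probably what was meant, but SAP 6.6 and Protocol 11.8.1 do not say it, so the clarification is still needed.

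Three stronger conclusions are tempting, and the documents do not support them.

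- *A reader might infer that the MI analysis is redundant on every reading.* The median-fill sentence leaves Reading C open, where MI would be a different analysis.
- *A reader might infer that the MI analysis tests nothing.* The imputation model is unspecified, and auxiliary variables could weaken the missing-at-random condition. In small samples the two methods also differ somewhat: with 21–22% missing at week 12, the median absolute gap was 0.6 min/day at 28 patients and 1.3 at 13. What stands is that the check does not test missing-at-random.
- *A reader might infer that the untested assumption favours the intervention.* That requires informative loss mainly in CR. With about 30% missing at week 12, loss linked to low activity and a truth of about 15, the estimate was 17.0 for CR-only loss, 14.9 for loss in both arms and 12.9 for usual-care-only loss.

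Missingness may also be light. Protocol 5.5 has the implant transmit activity automatically, so a missed app contact need not lose a week of data. The stopping of data at withdrawal and last contact remains, at an unstated rate.

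Finally, both documents call the study hypothesis generating, and at 13 patients the calculation in step 2 gives about 49% power, so a search for the shift that overturns a significant result may have nothing to overturn. This bears on how the analysis is reported: estimates and intervals at each shift remain useful.

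**Conclusion.** The conflict between SAP 6.6 with Protocol 11.8.1/11.12 and SAP 6.7 with Table 3.3 is real and should be settled before analysis. Unless the main analysis uses an across-patient fill, the planned MI analysis either repeats it or shares its missing-at-random assumption, and no other planned analysis departs from that assumption.

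The size is illustrative: 2.25 or 4.5 min/day of a 15 min/day target, at an assumed 15% or 30% loss in CR with full return to baseline. Both the rate and the mechanism are assumptions, and the sign could reverse. Both figures are smaller than one standard error at 28 patients, so this is an inexpensive improvement to the plan; it does not show that the primary result would be wrong.

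**What to change.** 1. In SAP 6.6, and in Protocol 11.11 and 11.12, state that main P1 uses all observed weekly values by likelihood, with no imputation of missing weeks. State that any median fill applies only to missing days within a patient's own week, never across patients.
2. Make the MI analysis in SAP 6.7 and Table 3.3 delta-adjusted. Impute missing weeks under missing-at-random, then shift the imputed values in steps of 5 min/day in the CR arm, and vary the shift in usual care as well. Report the estimate and 95% CI at each step, whether or not the main result is significant. A range reaching 15 min/day would cover a full return to baseline at week 12 under the planned effect. Name the variables in the imputation model, the number of imputations and the seed.
3. Correct the cross-reference in SAP 6.1.1 from 6.8 to 6.6.

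The cost is SAP and protocol wording and a modified MI program, with no change to conduct, data collection or sample size. The downside is one more assumption to explain, and wide intervals at the SAP's sample size.

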6.7 Sensitivity Analysis

The sensitivity Analysis will be considered for P1 ITT analysis:

Multilevel modeling after imputing missing data using MI: This sensitivity analysis will be performed with the same method as the main analysis, but with imputation for missing data as described above.

Multilevel modeling assumption not met: This sensitivity analysis will be performed if the Multilevel modeling assumptions are severely violated and data transformation is needed. If that is the case, we will run the multilevel model on the transformed data and the p-value will be compared to the main results. The estimated differences in slopes of trajectories and respective p-values will be presented.

Multilevel modeling of endpoints P1 after adjusting for baseline data: This sensitivity analysis will be performed using same methods as original analysis, but adjusting for the baseline mean in the model as a covariate. The significance of the treatment assignment variable will be tested. The estimated adjusted difference in slopes of trajectories and respective p-value will be presented and compared to the main results.

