## 11.5 COMPUTATION OF DERIVED VARIABLES

Weekly averages:

1. Baseline mean: Average of all measurements in a month prior to randomization.
2. Week 4 mean: Average of all measurements in week 4.
3. Week 8 mean: Average of all measurements in week 8.
4. Week 12 mean: Average of all measurements in week 12.
5. Change from baseline to Week 12 mean: Difference of week 12 mean from baseline mean.
- 1.

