4.1.2 Study Periods

For each enrolled participant, the study will consist of 3 Periods as follows:

- Screening/Enrollment Period – screening/enrollment begins after IRB approval prior to Baseline.
- Baseline Period - the first month (Day -30 – Day -1) of the study prior to the treatment period.
- Treatment Period - Following the baseline period, patients will be randomized 1:1 to either remote CR or usual care through the CR app and will be followed up for 12 weeks (Day 1 – Day 84).

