4.2 Sample Size and Power

Sample size was determined based on the following power calculations:

For aim 1, a sample size of 28 subjects with 1:1 randomization each measured at 4 time points provides 81.1% power to detect a 15 minute per day difference in PA between groups at week 12 with a standard deviation of 19 minutes per day within each group and a within subject correlation of 0.7. A test based on a mixed-model analysis is anticipated at a significance level of 0.05.

For aim 2, a sample size of 50 subjects with 1:1 randomization provides 80.2% power to detect an 8% difference in KCCQ score between groups with a standard deviation of 10 in KCCQ score within each group and an alpha of 0.05.

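### As plainly read, the baseline-adjusted sensitivity analysis of P1 cannot change the slope difference when data are complete, so it cannot show sensitivity to baseline imbalance

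*SAP*

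**What the plan says.** SAP 6.3 defines the P1 outcome as device-measured "daily PA obtained over the 1 month before randomization (baseline) and week 4, week 8, and week 12 after randomization", so baseline is itself a modelled response. The fixed effects are listed: "time (week of study), treatment group, and the interaction between treatment group and time will be handled as fixed effects". Time is continuous, with random intercepts and slopes for each patient. The reported result is the difference in slopes.

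SAP 6.7 lists three sensitivity analyses for P1. The third keeps the main method, "but adjusting for the baseline mean in the model as a covariate. The significance of the treatment assignment variable will be tested". It continues: "The estimated adjusted difference in slopes of trajectories and respective p-value will be presented and compared to the main results". Protocol 11.12 says nearly the same. Neither document names a baseline-by-time term, constrains the arms to a common baseline, or takes baseline out of the responses.

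The covariate is described in Protocol 11.5 as "Baseline mean: Average of all measurements in a month prior to randomization", and SAP 4.1.2 sets the baseline period as "the first month (Day -30 – Day -1) of the study prior to the treatment period". Protocol 11.8.1 instead gives a one-week baseline for P1. SAP 6.3 also says "If differences are noted with regard to baseline covariates adjusted analyses will be performed for the primary endpoint", without giving a model. SAP section 7 has tables for the imputed-data and transformed-data analyses (3.3 and 3.4) but none for this one.

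**The concern.** The purpose of a baseline-adjusted check is to show whether a chance difference in baseline activity is driving the result. Such a difference does enter the slope: with a within-patient correlation below 1, part of the gap regresses away after randomisation and appears as a difference in slopes. If the adjusted model cannot alter the slope difference, agreement between the two estimates is built in. A reader comparing them as SAP 6.7 directs would take that agreement as evidence of robustness. The trial is small, with 13 patients in SAP 4.1 and 28 in the Aim 1 power statement, so chance imbalance may not be trivial.

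**Working it through.** **Inputs.** SAP 4.2: SD 19 min/day, correlation 0.7, 28 patients, four time points, a "15 minute per day difference in PA between groups at week 12" of interest, alpha 0.05. SAP 6.3: the model. Taken as assumptions: times 0, 4, 8, 12, and equal correlation between all pairs of time points.

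**1. The plan's own figure.** The squared deviations of time sum to 36 + 4 + 4 + 36 = 80. The SD of a patient's slope is sqrt(19² × 0.3 / 80) = 1.1635. The standard error at 14/14 is 1.1635 × sqrt(2/14) = 0.4398. The target slope difference is 15/12 = 1.25, and 1.25/0.4398 - 1.96 = 0.882, giving power of 81.12% against the stated 81.1%. The stated power is therefore that of a slope-difference test.

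**2. The identity.** With complete data at common times, each patient reduces to a fitted intercept and a fitted slope.
- Main model: intercept on (1, arm); slope on (1, arm).
- Sensitivity model: intercept on (1, arm, baseline); slope on (1, arm).

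The slope regressors are a subset of the intercept regressors. Generalised least squares for the slope equation is then ordinary least squares, whatever the random-effects covariance. In both models the estimate is the difference in mean fitted slopes. This holds whether the covariate is the monthly mean or the monthly median. Over 500 arbitrary covariances with unequal arms, the largest discrepancy was below 5e-13.

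REML fits to single simulated datasets (assumed variance components; slope difference in min/day per week):

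| N | Baseline gap (min) | Main | Baseline added | Baseline and baseline-by-time added | p, main to baseline added |
|---|---|---|---|---|---|
| 13 | 13.2 | 0.530 | 0.530 | 0.865 | 0.56 to 0.60 |
| 28 | 4.5 | 0.569 | 0.569 | 0.651 | 0.27 to 0.33 |
| 50 | 11.4 | 0.714 | 0.714 | 1.114 | 0.059 to 0.082 |

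The first two estimates agree to eight decimals. The p-value moves only because the variance components are re-estimated.

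**3. What the check misses.** The 12-week slope-based difference weights the four arm differences by (-0.9, -0.3, 0.3, 0.9). Given a baseline gap d, the expected arm differences shift by (1, 0.7, 0.7, 0.7)d. The estimate therefore shifts by (-0.9 - 0.21 + 0.21 + 0.63)d = -0.27d, or -0.45d to -0.09d for correlations of 0.5 to 0.9. The SD of d is 19 × sqrt(1/n1 + 1/n2).

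That gives the baseline the noise of a single week. Suppose instead it averages four weeks with independent weekly errors (assumed). Between-patient variance is 0.7 × 361 = 252.7, and error variance is 108.3/4 = 27.1. The baseline SD is sqrt(279.8) = 16.7, and the regression of a later week on baseline is 252.7/279.8 = 0.903. The shift becomes 0.9 × (0.903 - 1)d = -0.087d.

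| Split | SD of d, week-like | Shift | SD of d, month | Shift |
|---|---|---|---|---|
| 14/14 | 7.18 | 1.9 min (13% of 15) | 6.32 | 0.55 min (3.7%) |
| 6/7 | 10.57 | 2.9 min (19%) | 9.31 | 0.81 min (5.4%) |

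**4. Response to imbalance.** In simulated complete-data trials (3,000 per setting), the regression of the estimate on d was -0.25 to -0.29 in the main and adjusted models alike. With baseline-by-time it was -0.03 to 0.02.

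**5. Missing weeks.** At 15% missing without imputation, the slope difference moved from 0.607 to 0.550 (N = 28) and from 0.596 to 0.619 (N = 13). Over 12 weeks that is about 0.7 and 0.3 min. At 20% missing, dependence on d was -0.295 (main) and -0.297 (adjusted) at 14/14, and -0.283 and -0.282 at 6/7. The estimate moves, but not because of imbalance.

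**The case against.** **The wording may allow more.** Neither document says main effect only. But SAP 6.3 names its interaction explicitly and SAP 6.7 names none, so a programmer following the text would add one term. The defect belongs to the plain reading, not to an explicit exclusion. Taking baseline out of the responses does not help: a main-effect covariate still leaves the slope difference over weeks 4 to 12 unchanged.

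**The p-value and the treatment coefficient can change.** True, so a reader should not infer that the whole comparison is guaranteed to agree; only the point estimate is fixed. The p-value shift could itself be misread as a correction. The treatment coefficient does absorb imbalance (7.36 to -4.28 in the N = 13 example). With time counted from baseline, however, it is the fitted week-0 difference, not the P1 contrast. The SAP does not state the time origin, and the phrase could mean the treatment slope term, so this part is a request for clarity and not a demonstrated error.

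**Data may be incomplete.** Multiple imputation is listed as a separate sensitivity analysis, so the main fit may use incomplete weeks. Exact equality then fails, but step 5 shows that the check stays uninformative about imbalance.

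**The shift may be small.** This stands. The 13% and 19% figures require a month-long baseline as noisy as one week, and independent weekly errors bring them to about 4% and 5%.

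**SAP 6.3 already allows adjusted analyses.** It gives no model, so this mitigates without curing.

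**Conclusion.** The point holds for the slope comparison. On the plain reading of SAP 6.7 and Protocol 11.12, the adjusted slope difference equals the main one exactly with complete data, including within each imputed dataset. With some weeks missing, it does not respond to imbalance. The comparison therefore cannot do what it is there for.

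The effect left unexamined ranges from about -0.09d to -0.27d over 12 weeks. For one SD of chance imbalance that is 0.55 to 1.9 min at 14/14 and 0.8 to 2.9 min at 6/7. Where it falls in that range depends on how much less noisy the baseline is than a single week, which the documents do not give.

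A reader might infer that the primary analysis is biased. It is not: the shift averages to zero over randomisations, and the P1 model is valid as it stands. This is one supportive analysis in a trial that SAP 6.5 calls hypothesis generating. It is worth correcting because the correction is cheap and the current output invites an unsupported claim of robustness.

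**What to change.** In SAP 6.7, for the sensitivity model only:

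- Keep the four responses, define time 0 as baseline, and add baseline-by-time next to baseline.
- Replace the sentence on the treatment assignment variable with a test of treatment-by-time.
- Use the same inference method for the adjusted and unadjusted slope differences: both from the mixed model, or both from regressions of per-patient slopes. If multiple imputation is used, make the imputed-data analysis (Table 3.3) the comparator.
- State that the adjusted-minus-main gap is descriptive. At 6/7 its SD is about 2 to 4 min (3.6 to 3.9 if the baseline is as noisy as one week, about 2.15 with independent weekly errors), so much of any gap will be noise.

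Make the same edit in Protocol 11.12 and add a table to SAP section 7. The cost is wording in two documents, one model term, a matched comparator and one table shell. No new data are needed, and the primary analysis does not change.
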